## **4. Study Population and Entry Criteria**

### **4.1 Number of Patients**

For the PK Cohort, at least 16 subjects will be enrolled to ensure 16 evaluable PK subjects at the Week 1 visit. For the Non-PK Cohort, approximately 84 additional patients will be enrolled in the study for a total of approximately 100 patients. PK Cohort patients who discontinue from the trial prior to either of the PK blood draws scheduled at Week 1/Visit 3

(or who otherwise do not have evaluable PK samples) will be replaced. Assuming an attrition rate of 15%, approximately 85 patients are expected to complete the 12-week trial.

## 4.2 Study Population Characteristics

Study participants will be 9 to 11 year-old male and female patients with mild, moderate, or severe acne vulgaris who are otherwise in good health. **For the PK Cohort**, mild, moderate, or severe acne vulgaris patients will be enrolled for PK characterization until at least 16 evaluable PK patients are enrolled. After 16 evaluable PK patients are enrolled, additional patients with moderate or severe acne vulgaris may continue to be enrolled in the PK Cohort.

## 4.3 Inclusion Criteria

The following are requirements for entry into the trial:

1. Written informed consent has been obtained from the patient's legally authorized representative prior to any trial related procedure
2. Written assent has been obtained from the patient (a minor) in accordance with local laws and IRB/IEC requirements
3. Written documentation has been obtained in accordance with the relevant country and local privacy requirements, where applicable (eg, Written Authorization for Use and Release of Health and Research Study Information for US centers)
4. Male or female patients, 9 to 11 years of age
5. Patients with acne vulgaris who have minimum of 20 but not more than 100 total inflammatory (papules, pustules, cysts, nodules) or noninflammatory (open or closed comedones) lesions on the face (including the nose) at screening and baseline
6. Patients with an acne grade of 2 (mild), 3 (moderate), or 4 (severe) using the IGA as assessed by the investigator at screening and baseline. **For the PK Cohort only:** after at least 16 PK patients are enrolled, additional patients with acne grades of 3 (moderate) or 4 (severe) using the IGA as assessed by the investigator at screening and baseline may continue to be enrolled in the PK Cohort unless specified by the Sponsor to refrain
7. Negative urine pregnancy test result for females at the Screening and Day 1 visits

8. Patient is in good health as determined by medical history, physical examination, and vital signs
9. Patient is willing to follow study instructions, complete study assessments without any assistance, and likely to complete all required visits

#### 4.4 Exclusion Criteria

The following are criteria for exclusion from participating in the trial:

1. Uncontrolled systemic disease(s)
2. Patients with severe cystic acne, acne conglobata, acne fulminans, or secondary acne (chloracne, drug-induced acne, etc)
3. Patients using systemic immunosuppressive drugs within 4 weeks prior to screening or anticipated use of any systemic therapy with the potential to affect acne during the trial
4. Any of the following topical procedures or treatments on the face occurring in the specified period prior to baseline (day 1):
  - 1 week: antibacterials (eg, clindamycin), salicylic acid, sulfur, sodium sulfacetamide, phototherapy devices (eg, ClearLight™), energy-based devices, adhesive cleansing strips (eg, Pond's® , Biore®), or cosmetic procedures (eg, facials, peeling, comedo extraction)
  - 2 weeks: anti-inflammatory drugs, corticosteroids, benzoyl peroxide-containing products (eg, benzamycin), retinoids, other topical acne treatments (eg, photodynamic therapy)  
note: No washout is required for alpha hydroxy acid products, astringents, antiseptics, devices used for cleansing and/or exfoliating the skin (eg, scrubs, pads, brushes), or preparations with alcohol for astringent effects, but they are not permitted at any time during the trial.
5. Any of the following systemic medications in the specified period prior to baseline (day 1):
  - 4 weeks: antibacterials (except penicillins used for 2 weeks or less)

- 6 months: other acne treatments (eg, isotretinoin, anti-androgens such as spironolactone)
6. Patients who are using or have used hormonal contraceptives and therapies
  7. Patients who have used topical dapsone within 1 month prior to the screening visit or oral dapsone within 2 months prior to the screening visit
  8. Patients who have any allergy or sensitivity to the study drug or its components
  9. Patients with underlying diseases or other dermatologic conditions such as, but not limited to, atopic dermatitis, perioral dermatitis or rosacea, which require the use of topical or systemic therapy that may interfere with the study assessments in the opinion of the investigator
  10. Skin abnormalities (other than acne vulgaris), excessive hair, or other physical characteristics in or around the test sites that could confound the trial results based on the investigator's judgment
  11. Patients who anticipate the need for surgery or hospitalization during the trial
  12. Females who are pregnant, nursing, or think they may be pregnant at the start of the trial
  13. Current enrollment in an investigational drug or device study, or participation in such a study within 30 days prior to screening for this trial
  14. Patients who have a clinically significant finding or condition, or are in a situation which, in the investigator's opinion, may put the patients at significant risk, may confound the trial results, or may interfere significantly with patient's participation in the trial
  15. Patients who have a medical history of hepatitis B, hepatitis C or human immune deficiency virus (HIV) infection
  16. Patients with a history of liver or kidney disease
  17. Patient who is an immediate family member (eg, partner, offspring, parents, siblings, or sibling's offspring) of an employee (eg, of sites, the Sponsor, or vendors) involved in the trial

## 4.5 Permissible and Prohibited Medications/Treatments

### 4.5.1 Permissible Medications/Treatments

Therapy considered necessary for the patient's welfare may be given at the discretion of the investigator. If concomitant medications may have an effect on trial outcomes, those medications should be administered in dosages that remain constant throughout the course of the trial. If the permissibility of a specific medication/treatment is in question, please contact the Sponsor.

Patients should maintain their usual skin care regimen, eg, non-medicated soaps, throughout the trial (with the exception of prohibited products).

### 4.5.2 Definition of Females of (Non-)Childbearing Potential and/or Acceptable Contraceptive Methods

For purposes of this study, all females will be considered of childbearing potential. If a patient misses a menstrual cycle, a urine pregnancy test must be performed.

If a female becomes pregnant during the study, the investigator will notify the sponsor immediately after the pregnancy is confirmed and the study treatment should be discontinued. The patient will be exited from the study after appropriate safety follow-up. The investigator will (1) notify the patient's physician that the patient was being treated with ACZONE 7.5%, and (2) follow the progress of the pregnancy. The investigator must document the outcome of the pregnancy and provide a copy of the documentation to the Sponsor.

### 4.5.3 Prohibited Medications/Treatments

The decision to administer a prohibited medication/treatment is done with the safety of the patient as the primary consideration. When possible, the Sponsor should be notified before the prohibited medication/treatment is administered.

Medications requiring washout ([Section 4.4](#)) must not be used during the study. Patients must not use topical drugs or treatments on acne affected areas. Patients must not use hormonal therapies or contraceptives.

For patients in the PK Cohort, use of any concomitant systemic medications that could affect PK outcomes is not permitted from 2 weeks prior to Day 1 through the Week 1/Visit 3 [Day 8 (+ 2 days)].

All patients are not permitted to use phototherapy devices, cosmetic procedures, or other topical acne treatments (eg, photodynamic therapy, laser therapy, or medicated soap).

Certain systemic medications (such as rifampin, anticonvulsants, St. John's Wort, and trimethoprim-sulfamethoxazole) may increase the formation of DHA, a metabolite of dapsone associated with hemolysis. With oral dapsone treatment, folic acid antagonists such as pyrimethamine have been noted to possibly increase the likelihood of hematologic reactions. Concomitant use of ACZONE 7.5% with drugs that induce methemoglobinemia such as sulfonamides, acetaminophen, acetanilide, aniline dyes, benzocaine, chloroquine, dapsone, naphthalene, nitrates and nitrites, nitrofurantoin, nitroglycerin, nitroprusside, pamaquine, para-aminosalicylic acid, phenacetin, phenobarbital, phenytoin, primaquine, and quinine may increase the risk for developing methemoglobinemia.

#### 4.5.4 Special Diet or Activities

All patients, and their legally authorized representative(s), will be instructed that throughout the trial they must refrain from:

- Intensively scratching their body at any areas of treatment
- Swimming or bathing up to 8 hours following drug application
- Tattooing their skin or body piercings to the areas of study drug application

Patients will be instructed to maintain their regular skin care regimen (with the exception of prohibited products) during the trial and must not use new products on treated areas while in the trial.

**For patients in the PK Cohort, from Day 1 through the Week 1/Visit 3 [Day 8 (+ 2 days)],** patients should not bathe, shower, swim, or wash face for at least 8 hours following administration of study drug.

## 5. Study Treatments

### 5.1 Study Treatments and Formulations

The study drug will be ACZONE 7.5% Gel (formulation number 11080X) consisting of dapson 7.5%, diethylene glycol monoethyl ether (DGME) [REDACTED], methylparaben, and purified water.

### 5.2 Methods for Masking/Blinding

This trial will be an open-label trial, and therefore blinding of the study drug is not required.

### 5.3 Method for Assignment to Treatment Groups/Randomization

Prior to initiation of study drug, each patient who has informed consent (provided by the legally authorized representative) will be assigned a patient number that will serve as the patient identification number on all study documents throughout the study.

All enrolled patients will receive ACZONE 7.5% treatment.

Study drug will be labeled with medication kit numbers generated by the Sponsor's Biostatistics group. An automated interactive web(-based) response system (IWRS) will provide the site with the specific medication kit number(s) for each enrolled patient at the time of study drug administration. Sites will dispense study drug according to the IWRS instructions. Sites will also log onto the IWRS at subsequent visits, as required, to obtain a study drug kit number for dispensing study drug. Sites will receive the IWRS confirmation notifications for each transaction. All notifications are to be maintained with the study source documents.

Assignment to the PK Cohort or the non-PK Cohort will be based on patient/legally authorized representative choice and the investigator's judgment.

### 5.4 Treatment Regimen and Dosing

#### 5.4.1 Conduct of the Study

For all patients, the first dose of study drug will be administered at the study site on Day 1. Administration of the first dose of study drug will need to be supervised by study site personnel.

To ensure maximal use conditions for the PK Cohort for the first 8 days, study drug will be provided in individual usage tubes containing approximately 2 grams each. One individual usage tube will be used each day for the first 8 days. The patients will be dispensed 1 kit with 14 tubes on Baseline/Day 1 (Visit 2). PK Cohort patients will return used study drug on Week 1/Visit 3.

For the first 8 days, study drug will be administered once-daily under maximal use condition (~2 grams/day) to the entire face, neck, upper chest, upper back and shoulders as instructed by the study site. The study drug should be rubbed in gently and completely. On Day 1, the study drug will be administered on site. From Day 2 through Day 7, the study drug will be administered in the morning at home by the patient's legally authorized representative. At the Week 1/Visit 3 [Day 8 (+2 days)], the study drug will be administered on site in the morning. After the Week 1/Visit 3, patients or the patient's legally authorized representative will apply a pea-sized amount of study drug in a thin layer to the patient's face, once-daily, at home for the remaining 11 weeks, the same as the dose regimen for the Non-PK Cohort. Acne-affected areas on the upper chest, upper back, and shoulders should also be treated with a thin layer during the final 11 weeks. Evaluable PK patients are defined as those that are administered at least 8 days of study drug under maximal use conditions, and provided PK samples for analysis without any major protocol deviations.

For the non-PK Cohort, patients or the patient's legally authorized representative will apply the study drug to the patient's entire face once-daily at home for the entire trial. The patients in the non-PK Cohort will be dispensed 60-gram pumps on Baseline/Day 1 (Visit 2), Week 4 (Visit 5) and Week 8 (Visit 6). Acne-affected areas on the neck, upper chest, upper back, and shoulders (where the patient can reach) should also be treated.

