### Study Objectives:

To evaluate the safety and tolerability of ACZONE Gel, 7.5% (hereafter referred to as ACZONE 7.5%) administered topically once-daily for 12 weeks in 9 to 11 year-olds with acne vulgaris

To evaluate the peak and trough plasma drug concentrations in 9 to 11 year-olds with acne vulgaris following once-daily dosing of ACZONE 7.5% under maximal use conditions for the first 8 days (+ 2 days)

To explore the efficacy of ACZONE 7.5% administered topically once-daily in 9 to 11 year-olds with acne vulgaris

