### Study Design

*Structure:* Multicenter, open-label, non-comparative trial

*Duration:* Patient participation is up to approximately 16 weeks from screening to trial exit; treatment duration is up to 12 weeks

*Study Treatment Groups:* ACZONE 7.5%

*Controls:* No control group

*Dosage/Dose Regimen:* All patients will receive treatment with ACZONE 7.5% once-daily

**Pharmacokinetic (PK) Cohort (at least 16 evaluable PK patients):** For the first 8 days (+ 2 days), study drug will be administered once-daily under maximal use condition (~2 grams/day) to the entire face, neck, upper chest, upper back and shoulders as instructed by the study site. The study drug should be rubbed in gently and completely. On Day 1, the study drug will be administered on site. From Day 2 through Day 7, the study drug will be administered in the morning at home by the patient's legally authorized representative. At the Week 1/Visit 3 [Day 8 (+2 days)], the study drug will be administered on site in the morning. After the Week 1/Visit 3, patients or the patient's legally authorized representative will apply a pea-sized amount of study drug in a thin layer to the patient's face, once-daily, at home for the remaining 11 weeks, the same as the dose regimen for the Non-PK Cohort. Acne-affected areas on the upper chest, upper back, and shoulders should also be treated with a thin layer during the final 11 weeks. Evaluable PK patients are defined as those that are administered at least 8 days of study drug under maximal use conditions, and provided PK samples for analysis without any major protocol deviations.

**Non-PK Cohort (approximately 84 patients):** Patients or the patient's legally authorized representative will apply a pea-sized amount of study drug in a thin layer to the patient's face once-daily for 12 weeks as instructed by the study site. Acne-affected areas on the upper chest, upper back, and shoulders should also be treated with a thin layer.

**Randomization/Stratification:** No randomization; all patients will receive ACZONE 7.5%. Assignment to PK or Non-PK Cohort will be based on patient/legally authorized representative choice and investigator's judgment.

**Visit Schedule** includes up to 7 scheduled study visits (see [Table 1](#) for further details):

- Visit 1: Screening (-30 to day -1)
- Visit 2: Day 1 (Baseline)a
- Visit 3: Week 1 (Day 8 + 2 days)
- Visit 4: Week 2 (±3 days)
- Visits 5 and 6: Weeks 4 and 8 (±7 days)

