**Table 2 Detailed Schedule of Procedures Specific to the PK Cohort**

Study Period	Screening	Baseline/Day 1	Day 2	Day 3	Day 4	Day 5	Day 6	Day 7	Day 8 (+ 2 Days) Week 1
Visit Number	Visit 1	Visit 2	NA	NA	NA	NA	NA	NA	Visit 3
PK Sampling									X a
On-Site dose administration		X							X b
At home dose administration b			X	X	X	X	X	X	

NA= not applicable; PK= pharmacokinetic.

a Two PK samples will be collected. Samples will be collected within 30 minutes prior to dosing in clinic in the morning and at approximately 10 hours post dose ( $\pm$  3 hour).

b Dosing for the PK cohort should always occur at approximately the same time in the morning.

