## 5.6 Treatment Administration

**For the PK Cohort**, at the Day 1 visit, patients and their legally authorized representative(s) will be instructed how to administer the study drug, and the study drug will be administered on site. For Days 2 through 7, study drug should be applied at approximately the same time in the morning (ie, before noon) at home by the patient's legally authorized representative. On Day 8 of the trial, study drug will be administered on site and in the morning.

After the skin on the face is gently washed and patted dry, legally authorized representative(s) of the patients will apply the contents of an individual usage tube containing 2 grams of study drug. The study drug will be applied to the patient's face, neck, upper chest, upper back, and shoulders. Wearing gloves, legally authorized representative(s) will spread the product on the patient's face, on the area between the mandibular line, and the hairline edge, taking care to avoid the areas around the eyes and the lips. The legally authorized representative(s) will also spread the study drug on the patient's neck, shoulders, upper chest, and upper back. New gloves will need to be used each day when applying the study drug. The product should be applied evenly to the entire face, neck, upper chest, upper back, and shoulders of the patient, and rubbed in gently and completely. All study drug should be rubbed in until no visible mass of the gel is observed on the surface of the skin. All patients and their legally authorized representatives will be provided with written instructions on the application of the study drug. Adherence to these instructions will be assessed at subsequent visits, with retraining performed as needed for noncompliant patients. Documentation of patient and legally authorized representative(s) training by site staff will be noted. See the non-PK Cohort section for information on PK Cohort patient dosing from the Week 1/Visit 3 until the end of study visit.

**For the Non-PK Cohort** at the Day 1 visit, patients and their legally authorized representative(s) will be instructed regarding how to administer the study drug for the

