#### 8.4.2 Baseline/Day 1 (Visit 2)

*Procedures (May be combined with the Screening Visit if no washout period is required)*

- IGA performed (should be performed before lesion count)\*
- Lesion count performed\*
- Inclusion/exclusion eligibility criteria re-evaluated\*
- Urine pregnancy test administered for females prior to administration of study drug\*
- Local tolerability assessed on the face prior to study drug administration on day 1
- Standardized photography performed at selected centers (make up must be removed at least 20 minutes prior to photography)
- Training on study drug application
- Study drug weighed
- Study drug administered on site and dispensed for at-home use for the PK Cohort. Patients will receive 2.0 gram tubes for daily application from Baseline to Day 8 (+ 2 days) and then 60-gram pumps will be dispensed from Week 1/Visit 3 onwards.
- Study drug administered on site and dispensed for at-home use for the non-PK Cohort. Patients will receive 60-gram pumps starting on Baseline/Day 1.
- Local tolerability performed on the face, postdose
- Adverse events recorded
- Concomitant medications and concomitant procedures recorded\*

\* These may not need to be repeated if the baseline and screening visits occur on the same day.

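### PK Cohort dosing text is inconsistent when Visit 3 falls on Day 9 or 10, and no PK rule links time since the last application to the peak/trough summary

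*Protocol*

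**What the plan says.** Visit 3 has a window of Day 8 to Day 10. The PK Cohort gives a predose sample and a sample about 10 h after the on-site dose. These are meant as steady-state trough and peak under maximal use (Protocol 1.4; PK DAP 5.1).

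The documents describe the 2 g dosing period in three ways.

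- **Up to the visit.** The PK objective refers to exposure "following once-daily dosing of ACZONE 7.5% under maximal use conditions for the first 8 days (+ 2 days"). The Summary says "For the first 8 days (+ 2 days), study drug will be administered once-daily under maximal use condition (~2 grams/day"). Protocol 8.4.2, the dispensing instruction, says "Patients will receive 2.0 gram tubes for daily application from Baseline to Day 8 (+ 2 days"), with pumps from Visit 3. SAP Table 5-11, footnote 2, expects one tube a day over the same extended period. The washing restriction in Protocol 4.5.4 runs to the visit as well: "For patients in the PK Cohort, from Day 1 through the Week 1/Visit 3 [Day 8 (+ 2 days")].
- **The first 8 days.** Protocol 5.4.1: "One individual usage tube will be used each day for the first 8 days". Protocol 3 and PK DAP 5.1 also limit maximal use to the first 8 days.
- **Home doses on Days 2–7 only.** "From Day 2 through Day 7, the study drug will be administered in the morning at home" appears in the Summary, Protocol 1.4, 3 and 5.4.1, SAP 4.1 and PK DAP 5.1. Protocol Table 2 ("Detailed Schedule of Procedures Specific to the PK Cohort") marks home doses for Days 2–7 and then goes straight to Visit 3. Protocol 5.6 adds: "On Day 8 of the trial, study drug will be administered on site and in the morning".

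An evaluable PK patient needs at least 8 applications (Protocol 3, PK DAP 5.1) or 8 days (Summary, 5.4.1) under maximal use, with no major protocol deviation. The PK population (Protocol 7.1, PK DAP 5.2) needs 8 days and evaluable samples; its definition has no deviation clause.

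**The concern.** No passage expressly states a home dose on Day 8 or Day 9 for a patient whose visit falls later. Section 8.4.2 implies both, and 5.4.1 implies Day 8. The sentence that sets the home-dosing days, and the detailed PK table, stop at Day 7. A site or family working from those would leave one or two undosed days before a late visit.

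The predose sample is timed only against the dose that follows it, so such a sample would still be called a trough. The PK DAP groups samples by nominal time and starts from all measured data. It calculates no PK parameters, so two concentrations per analyte in at least 16 children are the whole PK result. A missed day before the visit can only lower both concentrations, so the error would understate exposure in a maximal-use assessment.

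**Working it through.** **1. The plan's own figure.** Day 1 on site (1) + Days 2–7 at home (6) + Visit 3 on site (1) = 8 applications on 8 days. The threshold of 8 is reproduced, and it is met whichever day the visit falls.

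**2. Each reading applied to a late visit.**

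| Reading | Gap before trough, Day 9 visit | Gap, Day 10 visit | Applications including Visit 3 (Day 9 / Day 10) |
|---|---|---|---|
| Daily to the visit | 24 h | 24 h | 9 / 10 |
| First 8 days | 24 h | 48 h | 9 / 9 |
| Home doses on Days 2–7 only | 48 h | 72 h | 8 / 8 |

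All three satisfy the 8-application/8-day rule.

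**3. Effect on one patient.** Inputs: half-life 30–44 h for dapsone and N-acetyl dapsone (Protocol 1.2; none is given for the hydroxylamine). The documents give no absorption rate, so ka from 0.02 to 1.0 /h is assumed. The model is one compartment with equal doses superposed:

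C(t) = Σ ka/(ka − k) × [exp(−kΔ) − exp(−kaΔ)], where k = ln 2 / half-life and Δ is the time since each dose.

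k = 0.0158 /h at 44 h and 0.0231 /h at 30 h. The comparison is a Day 10 visit with prior doses on Days 1–8 (48 h gap) against Days 1–9. The two extremes for the trough, in relative units:

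- half-life 44 h, ka 0.02: 1 − 2.053/2.366 = 13.2% lower
- half-life 30 h, ka 1.0: 1 − 0.784/1.372 = 42.9% lower

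| ka (/h) | Trough loss, 44 h / 30 h | 10 h sample loss, 44 h / 30 h |
|---|---|---|
| 0.02 | 13.2% / 17.0% | 15.1% / 18.6% |
| 0.06 | 25.0% / 32.8% | 23.6% / 28.6% |
| 0.1 | 29.7% / 39.0% | 24.6% / 29.1% |
| 1.0 | 32.6% / 42.9% | 22.1% / 24.5% |

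The 10 h figures include the on-site dose. A Day 9 visit with the last home dose on Day 7, also a 48 h gap, gives trough losses of 13.8–43.1%. A 72 h gap (Day 10 visit, last home dose Day 7) gives 30.5–67.5% for the trough and 31.9–48.9% for the 10 h sample.

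**4. Effect on the mean of 16**, for 48 h gaps and assuming affected patients would otherwise have been average:

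- 1 affected: 0.132/16 = 0.8% to 0.43/16 = 2.7%
- 4 affected (illustrative): 4 × 0.132/16 = 3.3% to 4 × 0.43/16 = 10.8%

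**5. Would the compliance table show it?** Take doses on Days 1–8 and a Day 10 visit. SAP Table 5-11 gives 9/10 = 90% compliance if the undosed day is counted as missed, and 18 g/10 = 1.8 g/day. Neither value stands out, and neither says which day was missed.

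**The case against.** The case for leaving this alone is substantial. Section 8.4.2 gives tubes for daily use to Day 8 plus 2 days. With Visit 3 on site, the days in between can only be dosed at home. Nothing tells a family to skip a day of a once-daily drug while tubes remain, and 14 are supplied. Table 2 can be read as the calendar for a visit on the target day. This all stands. A reader might infer that the protocol instructs an undosed day, or that no text supports home doses on Days 8 and 9. The documents support neither inference.

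There are also generic safeguards. Tubes are returned and weighed and dosing is verified at Visit 3 (Protocol 8.4.3, 8.7). SAP Table 5-4 lists deviations, major deviations bar evaluability, and PK DAP 5.6 allows exclusions under regulatory guidance with reasons reported. One unused 2 g tube should be noticed. But neither a major deviation nor an evaluable sample is defined. A family that followed Table 2 has not clearly deviated. No rule carries a gap found at the visit into the peak/trough tables.

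Finally, the unseen procedure and laboratory manuals, or the written family instructions, may require dosing to the visit or record the last dose time. That cannot be ruled out.

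**Conclusion.** The point holds as an inconsistency of wording with a gap in the PK rules behind it. Daily dosing to the visit is the likely intent, but the shorter version appears in several operative places and gives a trough that is not a 24 h trough. For a 48 h gap the affected patient's trough is about 13–43% lower and the 10 h sample about 15–29% lower. This rests on the one-compartment model and the assumed absorption rate.

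A reader might go further and conclude that every late visit is affected or that the PK results as a whole are unreliable. The documents do not support that. Under 5.4.1 a Day 9 visit still has a normal 24 h gap, the number of late visits is unknown, and one affected patient moves the mean trough of 16 by only about 1–3%. The reported maximum falls only if the affected patient would have been the highest. The PK output is descriptive, and no stated threshold is shown to change. Priority is minor to moderate.

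**What to change.** **Dosing text.** Bring the Summary, Protocol 1.4, 3, 5.4.1 and 5.6, Table 2, and the matching SAP and PK DAP text into line with 8.4.2: one 2 g tube at home every morning from Day 2 through the day before Visit 3, then one on site at Visit 3. This uses 8–10 of the 14 tubes already supplied.

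**PK rule.** Record the date and time of the last home application at Visit 3, if the manuals do not already require it. In the PK DAP, derive time since the previous application, flag any patient not dosed the day before Visit 3, and show the peak/trough summary with and without those patients. This step can still be taken after dosing, wherever application dates were recorded.

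**Cost.** One repeated sentence, one corrected table, one recorded time, one derived variable and a second version of a short summary. Showing results both ways does not by itself require replacing a child under Protocol 4.1.
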